8.2. Analysis Populations

- Intent-to-Treat (ITT): All randomized subjects.
- Safety: All randomized subjects who received at least one dose of the Investigational Product.
- Per-Protocol (PP): All randomized subjects who received at least one dose of the Investigational Product AND completed the Day 30 clinic visit assessments AND have a Day 7 NT-proBNP value available for analysis.

All effectiveness analyses, including the primary endpoint and baseline characteristics will be performed on the ITT and Per-Protocol populations as further defined in the SAP. Safety analyses will be performed on the safety population.

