## 14. ANALYSIS POPULATIONS

**Intent-to-Treat (ITT):** ITT population will include all randomized subjects. The subjects in ITT population will be analyzed according to the treatment group they were originally randomized.

**Safety:** Safety population will include all randomized subjects who received at least one dose of Investigational Product (IP). The subjects in the Safety population will be analyzed and presented according to the actual treatment received.

**Per-Protocol (PP):** All randomized subjects who received at least one dose of the IP, completed the 30 Day clinic visit assessments and have a Day 7 NT-proBNP value available for analysis.

All effectiveness analyses, including the primary endpoint and baseline characteristics will be performed on the ITT and Per-Protocol populations. Safety analyses will be performed on the safety population.

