### 15.2.1 Primary Efficacy Analysis

The primary efficacy endpoint is the improvement in a composite/combined morbidity/mortality endpoint at 30 days using the Finkelstein Schoenfeld method. The analysis of the primary efficacy endpoint will be conducted for the ITT and PP populations. Each component of the primary endpoint will be compared in pairwise fashion hierarchically. Each patient is compared to all other patients with respect to each of the following endpoints hierarchically. The algorithm is as follows when doing a pairwise comparison of Patient B to Patient A:

- CV death at 30 days:
  - if Patient A survives to 30 days and patient B dies before 30 days, then score = -1 for Patient B
  - if Patient B survives to 30 days and patient A dies before 30 days, then score = +1 for Patient B
  - if both patients survive or if both die , then move to the comparison on the next component.
- HF hospitalization at 30 days:
  - if Patient A is not hospitalized for worsening heart failure (WHF) and patient B is, then score = -1 for Patient B
  - if Patient A is hospitalized for WHF and patient B is not, then score = +1 for Patient B
  - if both patients are not hospitalized or if both are hospitalized, then move to the comparison on the next component.
- Urgent ED/Clinic visit at 30 days for WHF (defined as IV diuretics, augmentation of or new administration of metolazone)
  - if Patient A does not have an Urgent/ED visit for WHF and patient B does have a visit, then score = -1 for Patient B
  - if Patient A does have an Urgent/ED visit for WHF and patient B does not have a visit, then score = +1 for Patient B
  - if both patients have an Urgent/ED visit for WHF, then move to the comparison on the next component.

- if both patients do not have an Urgent/ED visit for WHF, then move to the comparison on the next component.
- Percent Change in NT-proBNP from baseline at 7 days (without imputation):
  - if Patient A's change from baseline at 7 days in NT-proBNP < Patient B's change from baseline at 7 days in NT-proBNP, then score = -1 for Patient B
  - if Patient A's change from baseline at 7 days in NT-proBNP > Patient B's change from baseline at 7 days in NT-proBNP, then score = +1 for Patient B
  - If tied, score=0 for Patient B.

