A -1/0/1 score is created for Patient B vs. every other patient in the study, so if there are  $n$  total patients in the study, then patient B is assigned  $n$  -1/0/1 scores (including, for completeness, a score of 0 when patient B is compared to themselves). Similarly, every other patient in the study is also assigned  $n$  -1/0/1 scores.

For each patient  $i$ , the sum of all -1/0/1 scores assigned to that patient is calculated and is denoted as  $U_i$ . If  $n1$  and  $n2$  are the number of patients in the experimental and control arms, respectively, then the lowest possible value of  $U_i$  that a given patient can experience is  $-(n1 + n2 - 1)$ , which is achieved if the given patient scored a -1 versus all other  $(n1 + n2 - 1)$  patients in the study; similarly, the largest possible of  $U_i$  that a given patient can experience is  $+(n1 + n2 - 1)$ .

The numerator of the estimate of  $T$  (the Finkelstein-Schoenfeld test statistic) is the sum of the  $U_i$  across patients assigned to the experimental treatment. i.e.,

$$\sum_{i=1}^n D_i U_i$$

where  $U_i$  is the sum of the -1/0/1 scores for the  $i^{\text{th}}$  patient in the sample,  $D_i$  is the indicator of the treatment group to which the  $i^{\text{th}}$  patient was randomized ( $D_i = 0$  for control and  $D_i = 1$  for experimental) and  $n$  is the total sample size.

The denominator of  $T$  is:

$$\sqrt{\frac{n1 * n2}{n * (n - 1)} \sum_{i=1}^n U_i^2}$$

where (a)  $n1$  and  $n2$  are the number of patients in the experimental and control arms, respectively; (b)  $n$  is the total sample size ( $= n1 + n2$ ); and (c)  $U_i$  is the sum of the -1/0/1 scores for the  $i^{\text{th}}$  patient in the sample. The test statistic follows a standard normal distribution; the two-sided p-value is the area in the upper and lower tails of  $T$  on the standard normal curve.

The primary efficacy endpoint will be repeated for the ITT and PP analysis populations using the Day 3 NT-proBNP value (instead of the Day 7 NT-proBNP value). The Day 3 NT-proBNP value will be used for calculating the percent change from baseline as follows:

- Percent Change in NT-proBNP from baseline at 3 days:
  - if Patient A's change from baseline at 3 days in NT-proBNP < Patient B's change from baseline at 3 days in NT-proBNP, then score = -1 for Patient B
  - if Patient A's change from baseline at 3 days in NT-proBNP > Patient B's change from baseline at 3 days in NT-proBNP, then score = +1 for Patient B

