  - If tied, score=0 for Patient B.

A listing of each endpoint for the composite will be presented for the ITT population.

A sensitivity analysis will be conducted where the primary efficacy endpoint analysis will be conducted on the ITT and PP analysis population and will exclude patients with normal NT pro-BNP values (defined as <125 pg/mL) at baseline. Results will be descriptively compared to the primary efficacy endpoint analysis on the ITT and PP population.

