#### **15.2.1.1 INDIVIDUAL ANALYSIS OF PRIMARY ENDPOINTS**

Each component of the primary efficacy endpoint will be analyzed individually for the ITT and PP populations between treatment groups.

- CV death at 30 days:

CV death will be summarized by counts and percentages for Furoscix on-body Infusor and Continued medical therapy.

In addition, comparison of the proportion of death among Furoscix on-body Infusor and Continued medical therapy will be conducted using chi-square test. Proportion of death in each treatment group and also the proportion difference along with its corresponding 95% CI and p-value will be presented at Day 30.

If any of the cells has expected frequency count less than 5 then the comparisons will be performed through a Fisher exact test. The p-value will also be presented using Chi-square/Fisher exact test to identify statistically significant differences in proportion of deaths for Furoscix on-body Infusor vs Continued medical therapy.

- HF hospitalization at 30 days:

The analysis of HF hospitalization will be conducted similar to CV death at 30 Days.

- Urgent ED/Clinic visit at 30 days for WHF (defined as IV diuretics, augmentation of or new administration of metolazone):

The analysis of Urgent ED/Clinic visit for worsening heart failure will be conducted similar to CV death at 30 Days.

- Percent Change from baseline in NT-proBNP at Day 3, at Day 7 and at Day 30:

The percent change in NT-proBNP from baseline across timepoints will be analyzed using a GEE model which includes change in NT-proBNP from baseline as the response variable, treatment, timepoint and treatment by timepoint interaction as fixed effects and baseline value of NT-proBNP as the covariate. An unstructured covariance matrix structure will be used to model the within subject errors. Least square means, corresponding 95% Confidence Interval (CI) and standard error (SE) from the model will be presented for Furoscix on-body Infusor and Continued medical therapy. The LS means estimate, standard error, 95% CI, and p-value for the treatment difference will also be presented.

Additionally, non-parametric correlation (Spearman's Rank) analysis of percent change from baseline in NT-proBNP at Day 3, 7 and 30 and number of doses (Infusion) will be performed. The significance of correlation coefficient will be tested using a t-test.

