### 15.2.2 Secondary Efficacy Analysis

The observed and change from baseline values of secondary endpoints will be summarized using descriptive statistics such as n, mean, median, minimum, and maximum for continuous variables and count and percentages will be provided for categorical variables by treatment group and overall. Individual subject data listings for all secondary endpoints will be presented for ITT population. Secondary endpoints will also be compared between treatment groups on the ITT, and PP population; a two-sided 0.05 level of significance will be used for each endpoint:

- Days alive and heart failure event-free (hospitalization for heart failure or ED visits for heart failure) over 30 days will be compared using the non-parametric Wilcoxon rank sum test.
- Changes from baseline in patient global assessment via visual analog scale (VAS) across follow-up timepoints will be analyzed using a GEE model with treatment arm, timepoint and treatment by timepoint interaction as fixed effects, and the baseline value

of VAS as covariates. An unstructured covariance matrix structure will be used to model the within subject errors.

- Changes from baseline in composite congestion score across follow-up timepoints will be analyzed using a GEE model with treatment arm, and timepoint and treatment by timepoint interaction as a fixed effect, and the baseline value of congestion score as covariates. An unstructured covariance matrix structure will be used to model the within subject errors.
- Changes from baseline in 5-point Current Dyspnea Score across follow-up timepoints will be analyzed using a GEE model with treatment arm, and timepoint and treatment by timepoint interaction as a fixed effect, and the baseline value of 5-point Current Dyspnea Score as covariates. An unstructured covariance matrix structure will be used to model the within subject errors.
- A repeated measures analysis of 7-point Dyspnea Score across follow-up timepoints will be analyzed using a GEE model with treatment arm, and timepoint and treatment by timepoint interaction as a fixed effect. An unstructured covariance matrix structure will be used to model the within subject errors.

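### Per-Protocol membership requires a completed Day 30 visit, so the PP mortality analyses can hardly register a death, yet neither document ranks PP below ITT

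*SAP*

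**What the plan says.** SAP section 14 requires a PP subject to have had at least one dose of IP and to have "completed the 30 Day clinic visit assessments and have a Day 7 NT-proBNP value available for analysis". Protocol 8.2 sets the same conditions: "completed the Day 30 clinic visit assessments AND have a Day 7 NT-proBNP value available for analysis". Neither treats a death before the visit differently from a missed visit.

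The SAP then uses PP throughout the efficacy analysis:

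- Section 14: "All effectiveness analyses, including the primary endpoint and baseline characteristics will be performed on the ITT and Per-Protocol populations".
- Section 15.2.1, on the Finkelstein-Schoenfeld test whose first tier is CV death: "The analysis of the primary efficacy endpoint will be conducted for the ITT and PP populations".
- Section 15.2.1, on the repeat: "The primary efficacy endpoint will be repeated for the ITT and PP analysis populations using the Day 3 NT-proBNP value".
- Section 15.2.1.1, which includes a chi-square or Fisher test of CV death: "Each component of the primary efficacy endpoint will be analyzed individually for the ITT and PP populations between treatment groups".
- Section 15.2.2, which includes days alive and HF event-free: "Secondary endpoints will also be compared between treatment groups on the ITT, and PP population".

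No section of either document orders the two populations or says what follows if they disagree. SAP 15 makes no multiplicity adjustment. ITT gets some preference in reporting only, for example "A listing of each endpoint for the composite will be presented for the ITT population" in section 15.2.1.

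**The concern.** Membership of the analysis set depends on the outcome being analysed. The first tier separates a pair only when one patient survives to Day 30 and the other does not. A set restricted to people who attended the Day 30 visit contains almost no such pairs, whatever the treatment does to mortality. A 0 versus 0 result in PP would then reflect the definition and say nothing about the drug.

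Because PP stands level with ITT, a reader could take a PP composite that ignores deaths as independent support for ITT. If deaths fall on Furoscix, PP could look better than ITT for that reason alone.

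**Working it through.** **Inputs from the documents.** 51 subjects, 34 Furoscix and 17 control (SAP 4; 51 × 2/3 = 34 and 51 × 1/3 = 17). Two-sided alpha is 0.05 (SAP 15). The Finkelstein-Schoenfeld statistic is as in SAP 15.2.1. The Day 30 visit window is ± 5 days (Protocol 6.2.9). No power calculation, event rate or effect size is given, so death counts and NT-proBNP effects below are assumptions. Two-arm PP figures also assume that controls can belong to PP (step 6).

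**1. CV-death test.** Fisher exact, two-sided:

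| Deaths, Furoscix v control | ITT p | PP table |
|---|---|---|
| 0/34 v 1/17 | 0.333 | 0/34 v 0/16 |
| 0/34 v 2/17 | 0.107 | 0/34 v 0/15 |
| 0/34 v 3/17 | 0.033 | 0/34 v 0/14 |
| 1/34 v 0/17 | 1.0 | 0/33 v 0/17 |
| 2/34 v 0/17 | 0.547 | 0/32 v 0/17 |
| 3/34 v 0/17 | 0.542 | 0/31 v 0/17 |

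In PP, Fisher p is 1.0 in every row, and chi-square cannot be computed because expected counts are zero.

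**2. Composite, deaths only.** With a full ranking of n = 51, ΣU² = 51 × (51² − 1)/3 = 44,200. The denominator of T is √[34 × 17/(51 × 50) × 44,200] = 100.1.

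- One control death loses to all 34 Furoscix subjects: z shifts by +34/100.1 = +0.34.
- One Furoscix death scores −50, and the other 33 Furoscix subjects gain 1 each: (−50 + 33)/100.1 = −0.17.
- Three control deaths give about 3 × 34/100.1 = 1.02, short of 1.96. In simulation, mean z reaches 2.04 only at about 6 of 17 control deaths.
- The PP statistic stays at 0 on average in all these cases.

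**3. Composite, deaths plus an NT-proBNP difference.** Simulation assumptions: normally distributed change, no HF events, deaths unrelated to NT-proBNP, and decedents' NT-proBNP missing and scored 0. Approximate percentage of trials in which the two populations disagree at 0.05:

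| NT-proBNP shift (SD) | 0 | 0.3 | 0.65 | 1.0 | 1.3 |
|---|---|---|---|---|---|
| 1 Furoscix death: PP significant, ITT not | 1 | 5 | 9 | 6 | 1 |
| 2 Furoscix deaths: PP significant, ITT not | 2 | 9 | 20 | 13 | 3 |
| 1 control death: ITT significant, PP not | 2 | 8 | 11 | 5 | 1 |

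Entries are good to about one percentage point. The peak is near 0.65 SD because the composite z with no deaths is then 2.05, next to the critical value. At that shift, one and two Furoscix deaths lower mean ITT z to about 1.82 and 1.58, while PP stays near 2.0.

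**4. Days alive.** Two control deaths at Day 15 cost 2 × 15/17 = 1.76 days in the ITT control mean, and nothing in PP.

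**5. Deaths that escape exclusion.** A subject seen on Days 25 to 29 can die before Day 30 and stay in PP. With visits spread evenly over Days 25 to 35 and deaths evenly over 30 days, the share is (5 + 4 + 3 + 2 + 1)/(30 × 11) = 4.5%. If every visit were on Day 25 it is 5/30 = 16.7%. Deaths concentrated late would raise both. Follow-up assessments done at withdrawal (Protocol 4.3) are a second possible route. Dropping only the Day 30 condition would not cure the problem: the Day 7 NT-proBNP condition still removes deaths before Day 7, about 7/30 = 23% under an even spread.

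**6. The dose condition.** Controls follow the schedule without study product (Protocol 6.2.2). Read literally, at least one dose of IP excludes all of them. Then n2 = 0, the numerator and denominator of T are both 0, and no PP test exists.

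**The case against.** The strongest reply is that ITT is intact. It keeps all deaths, runs the same tests and lists every component, and SAP 15.1 tabulates membership of each population. This is also an unpowered pilot with no success decision tied to PP, and screening excludes suspected high-risk instability (Protocol 4.2), so deaths may be few or none. All of that stands, and it confines the harm to interpretation of PP. It does not remove the point, because one stated objective is to refine endpoints and analytical methods for a pivotal trial, and this definition could be carried forward.

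It is also fair to say that the disagreement rates depend heavily on the assumed effect. The values at 0.65 SD are close to the worst case and should not be quoted as typical.

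A reader might infer that the plan hides mortality, or that PP empties the whole hierarchy. The documents support neither. HF hospitalizations and urgent visits that resolve before the required visits stay in PP, so tiers 2 and 3 still contribute, although subjects too ill to attend drop out.

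Finally, the literal dose condition would prevent any two-arm PP result, so the two defects do not add up. The mortality problem appears once the dose condition is read or reworded to admit controls.

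**Conclusion.** The point holds for PP only. By its own membership rule, PP cannot meaningfully compare mortality: the CV-death tier, the Day 3 repeat of the composite, the CV-death test, and the survival part of days alive and HF event-free are insensitive to nearly all deaths before Day 30. Neither document tells the reader to give PP less weight than ITT.

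The practical size is modest and conditional. The CV-death verdict differs only at an extreme imbalance such as 0 versus 3 of 17 (18%). On deaths alone both composites would usually be non-significant. The composites could disagree in up to about one trial in ten with one Furoscix death and one in five with two, under the least favourable of the shifts examined, and far less often at shifts of 0 or 1.3 SD. Without deaths this mechanism has no effect. It is worth correcting because the repair is short, and because a 0 versus 0 mortality result of equal standing invites a wrong reading.

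**What to change.** 1. In SAP 14 and 15.2.1 add: *ITT is the primary population for the composite and each of its components; PP analyses are supportive.* Align Protocol 8.2 at the next amendment.
2. Label the present set (Day 30 visit completed and Day 7 NT-proBNP available) a completer set and use it only for NT-proBNP. Do not run the composite, its Day 3 repeat, the CV-death test or days alive on it. SAP 15.2.1.1, 15.2.2 and 15.4, and the baseline NT-proBNP sensitivity analysis in 15.2.1, also name PP and need conforming edits.
3. Reword the IP-dose condition so that it applies to the Furoscix arm only and controls can belong to the set.

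Redefining PP by eligibility and major deviations is optional. It would reverse a choice made in Amendment 5 and needs a deviation classification that neither document contains. The scoring of missing NT-proBNP also affects ITT and should be raised as a separate point.

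Cost: a few sentences and no new data. The SAP takes precedence (SAP 15), so it can be corrected first. The protocol change needs IRB approval (Protocol 9.2.2). The loss is one supportive analysis of the composite and of mortality, and the remaining secondary endpoints would rest on ITT.

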## 15. STATISTICAL ANALYSIS

This is a multicenter, randomized, open label, controlled study evaluating the effectiveness and safety of the Furoscix Infusor versus continued medical therapy in patients with chronic heart failure and fluid overload requiring augmentation in diuretic therapy outside of the acute care setting. The SAP takes precedence over the protocol.

Unless otherwise specified, all baseline data, including demographic data and other clinical characteristics will be compared using descriptive statistics grouped by treatment group (Furoscix On-Body Infusor vs Continued Medical Therapy for Worsening Heart Failure). Change from baseline is the absolute change, unless stated otherwise; which then will be percentage change from baseline. Tables will include footnotes indicating definition implemented. Continuous data will be summarized by reporting the number of observations, mean, standard deviation, minimum, median, and maximum values. Categorical data will be described using frequency tables showing the number and percentage of subjects falling within a particular category. Shift tables will be given where appropriate to show change at follow-up compared to baseline values.

Between-group analyses of baseline characteristics will employ descriptive statistics. Mortality and morbidity events will be assessed using appropriate statistical tests. The primary endpoint will be compared between treatments using the Finkelstein-Schoenfeld Method, comparing components of the composite endpoint between patients hierarchically. Given the nature of the study, there will be no imputation of missing data on endpoints.

The primary endpoints including CV death at 30 days, HF hospitalization at 30 days, Urgent ED/Clinic visit at 30 days for WHF (defined as IV diuretics, augmentation of or new administration of metolazone), and change in NT-proBNP from baseline at 7 days will also be summarized and analyzed separately.

In general, secondary efficacy with follow-up timepoints will be analyzed using Generalized Estimating Equations (GEE) models.

Statistical tests will be performed at a two-sided alpha level of 0.05, unless otherwise specified. Given the nature of the study, there will be no adjustment for multiple comparisons.

## 15.1 Analysis of Baseline Characteristics

- **Subject Disposition.** The number and percentage of subjects consented but screen failed, enrolled, randomized, lost-to-follow-up, withdrawn (and reasons) and completed will be presented.  
A listing of subject disposition will also be presented.
- **Analysis Populations.** The number and percentage of subjects in each of the analysis populations will be presented for all randomized subjects.  
A listing of analysis populations will be presented for ITT population.
- **Demographic and Baseline Characteristics.** Demographics (Age, Gender, Race, Ethnicity, NYHA Class, BMI) will be summarized by treatment group, and overall for ITT and PP populations. Categorical variables (Gender, Race, Ethnicity, and NYHA Class) will be summarized using frequency count and percentage while continuous variables (Age, and BMI) will be summarized using descriptive statistics.  
Demographic and baseline data will be listed using ITT Population.
- **Vital Signs.** Descriptive statistics by treatment group of systolic blood pressure, diastolic blood pressure, heart rate, respiration rate, weight will be presented for ITT population.  
Vital signs data will also be listed using ITT population.
- **NYHA Class.** A shift table comparing the change in the NYHA Class from baseline to post-baseline visits will be presented by treatment group for ITT population.  
NYHA class data will also be listed using ITT population.
- **Medical History and CV History.** Medical history will be coded using Medical Dictionary for Regulatory Activities (MedDRA) version 23.1 and summarized using the number and percentage of subjects within each System Organ Class (SOC), and Preferred Term (PT) by treatment group for Safety population. Listing of medical history will also be presented.  
The CV history will be summarized using the number and percentage of subjects within each category by treatment group for ITT population. Listing of CV history for subjects in the ITT Population will be provided.
- **Cardiopulmonary Examination.** The number and percentage of subjects within each parameter of each category by treatment group will be presented for ITT population.  
Listing of cardiopulmonary examination will also be presented for same population.
- **Ejection Fraction.** The number and percentage of subjects within a category of Imaging Modality and descriptive statistics of LVEF (%) will be presented by treatment group for ITT population. Listing of ejection fraction will also be presented.

Continuous data will be compared between treatment groups using a Two-Independent-Sample T-Test. In case when the data is non-normal (based on the Shapiro-Wilk normality

test with a p-value <0.15), the nonparametric Wilcoxon Rank Sum test will be applied. The categorical data will be compared between treatment groups using Chi-Square test for Two-Way tables. In case when frequencies below five are met for more than 20% of the cells, a Fisher's exact test will be applied.

